5.8.4. Subgroup Efficacy Analysis and Exploratory Efficacy Analysis

Subgroup efficacy analyses will be performed based on the following factors, respectively:

- gender (Male, Female)
- age group (<65, ≥65)
- race (White, Non-white)

- geographical region (North American, Europe and Rest of World)
- number of prior systemic therapies (1, >1)
- prior HHI (Progression/Lack of Response, Intolerant)
- histologic subtype (Nodular, Infiltrative, Other)

However, due to small sample sizes, the subgroup analysis will be exploratory in nature.

In Group 2 patients who experience objective responses, the number of patients who remain with unresectable BCC and the number of patients from whom BCC becomes resectable (complete gross resection) will be tabulated.

5.9. Analysis of Safety Data

The analysis of safety and tolerance will be performed on the SAF. The summary of safety results will be presented by group and combined.

5.9.1. Adverse Events

The verbatim text, the primary system organ class (SOC), and the preferred term (PT) will be displayed in subject listings. Summaries that include frequencies and proportions of patients reporting AEs will include the SOCs and the PTs .

Period of observation: The observation period will be divided into three segments: pre-treatment, on-treatment and post-treatment.

- The pre-treatment period is defined as the time between when the subjects give informed consent and before the start of cemiplimab treatment.
- The on-treatment period it is defined as the time from the first dose of cemiplimab up to 105 days after the last dose of cemiplimab;
 - For patients who started cemiplimab as re-treatment more than 45 days after the last dose of regular cemiplimab treatment, the on-treatment period ends at the earlier day of 105 days after the last dose of regular cemiplimab or 1 day before the first dose of cemiplimab re-treatment;
 - For patients who started cemiplimab re-treatment within 45 days of their last regular cemiplimab treatment, the re-treatment is considered as a part of the regular treatment. That is, the on-treatment period ends at 105 days after the last dose of cemiplimab re-treatment;
 - For patients who started new anti-cancer systemic therapy, the on-treatment period ends at the earlier day of 105 days after the last dose of regular cemiplimab or 1 day before the first dose of new anti-cancer systemic therapy.

- The post-treatment period is defined as the time starting one day after the end of on-treatment period.

Definitions:

- Pre-treatment AEs are defined as AEs that developed during the pre-treatment period and are not treatment-emergent as defined below.
- Treatment-emergent AEs (TEAEs) are defined as AEs that developed or worsened during the on-treatment period and treatment-related AEs that occur during post-treatment period.
- Post-treatment AEs are defined as AEs that developed or worsened during the post-treatment period and are not considered drug related by the investigator.

The focus of adverse event reporting in the CSR will be on TEAEs. For details on handling missing data and partial dates, see Section 6.

Summaries of TEAEs will include: TEAEs, Treatment related TEAEs, Serious TEAEs, Treatment-related Serious TEAEs and treatment-emergent AESI. For TEAEs, the following will be summarized:

- The number and proportions of patients reporting at least 1 TEAE, presented by SOC and PT
- TEAEs by severity (CTCAE, latest available version), presented by SOC and PT
- Grade ≥ 3 TEAEs by SOC and PT
- TEAEs related to treatment, presented by SOC and PT
- Grade ≥ 3 treatment-related TEAEs by SOC and PT
- TEAEs leading to permanent treatment discontinuation, presented by SOC, PT and CTCAE NCI
- TEAEs leading to death, presented by SOC and PT
- IRR by SOC, PT and CTCAE NCI
- Treatment-emergent potential irAEs based on sponsor list by SOC, PT and NCI and by Composite term, PT and NCI
- Treatment-emergent identified irAEs based on sponsor list by SOC, PT and NCI and by Composite term, PT and NCI

For each TEAE summary presented by SOC and PT, the summary table will be sorted by decreasing frequency of SOC and PT. For TEAE summary presented by PT, the summary table will be sorted by decreasing frequency of PT.

For TEAE listings, the following variables will be displayed:

- Verbatim Term, SOC, PT
- AE start date and end date (and corresponding study day)
- Relationship to study drug: unrelated or related
- Seriousness (Serious AE or not)
- National Cancer Institute-Common Terminology Criteria for Adverse Events (NCI-CTCAE) grade
- Action taken
- Treatment for AE: none, medication, procedure/surgery
- Outcome

Pre-treatment AEs and post-treatment AEs will be listed separately.

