8.1.5. Retreatment

For patients (Group 1 or Group 2) who complete 9 cycles of treatment without disease progression and subsequently experience disease progression during the follow-up period (follow-up visits 1 through 7 only) without any intervening systemic anticancer therapy, resumption of treatment with cemiplimab IV 350 mg Q3W will be allowed per [Table 5](#) (four 12-week cycles). Prior to resumption of cemiplimab treatment, patients must be re-consented (including resigning informed consent) and must repeat all screening activities (with the exception of providing new archived pathology material, research biopsies, or brain MRI), and the investigator must confirm that the patient still meets all eligibility criteria (other than the exclusion regarding prior treatment with anti-PD-1). Such patients will resume cemiplimab 350 mg Q3W monotherapy treatment for 48 weeks (maximum 4 retreatment cycles; 12 weeks per cycle), as per the schedule of events in [Table 5](#). However, PK, ADA, research blood samples, and research tumor biopsies (exploratory “Tumor Biopsies” for Group 2) are not required for these patients during retreatment. In response to AESI like anaphylaxis or hypersensitivity, ADA samples closer to the event may be collected and analyzed, based on the judgement of the medical investigator and/or medical monitor.

After retreatment, patients will be followed quarterly for survival and tumor treatment status, if available, until death. Follow-up status may be determined at clinic visits or via telephone contact with the patient, a family member of the patient, or the physician.

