10.4.5.1. Adverse Events

Definitions

For safety variables, 3 observation periods are defined:

- The pretreatment period is defined as the time from signing the ICF to before the first dose of study drug.
- The on-treatment period is defined as the time from first dose of study drug to 105 days after the last dose of study drug.
- The post-treatment period is defined as the time starting 1 day after the on-treatment period.

Treatment-emergent adverse events (TEAEs) are defined as AEs that are not present at baseline or represent the exacerbation of a pre-existing condition during the on-treatment period and treatment-related AEs that occurs any time after the first cemiplimab dose.

Note regarding retreatment: For patients who receive cemiplimab as retreatment, which starts more than 45 days after their last regular cemiplimab treatment, the on-treatment period ends at the earlier day of 105 days after the last regular cemiplimab dose and the day before their first cemiplimab retreatment dose. Cemiplimab retreatment that starts within 45 days after the last regular cemiplimab dose will be considered as regular cemiplimab treatment.

Analysis

All AEs reported in this study will be coded using the currently available version of the Medical Dictionary for Regulatory Activities (MedDRA[®]). Coding will be to lowest level terms. The verbatim text, the preferred term (PT), and the primary system organ class (SOC) will be listed.

Summaries of all TEAEs by group will include:

- The number (n) and percentage (%) of patients with at least 1 TEAE by SOC and PT
- TEAEs by severity (NCI-CTCAE, version 4.03 grade), presented by SOC and PT
- TEAEs by outcome
- TEAEs by relationship to experimental treatment (related, not related), presented by SOC and PT

Deaths and other SAEs will be listed and summarized by group.

Events of NCI-CTCAE Grade 3 and Grade 4 severity will be summarized by group.

Treatment-emergent adverse events leading to permanent treatment discontinuation will be listed and summarized by group.

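### When cemiplimab retreatment starts more than 45 days after the last regular dose, the SAP's TEAE tables count related retreatment AEs but leave out unrelated ones

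*SAP*

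**What the plan says.** Protocol 8.1.5 allows retreatment for patients who finish nine cycles without progression and then progress during follow-up visits 1 to 7: "Such patients will resume cemiplimab 350 mg Q3W monotherapy treatment for 48 weeks", in at most four 12-week cycles.

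SAP 5.9.1 divides safety observation into pre-treatment, on-treatment and post-treatment periods. On-treatment normally runs to 105 days after the last dose. There are two retreatment rules:

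- **Gap of 45 days or less.** Retreatment is part of regular treatment, and on-treatment runs to 105 days after the last retreatment dose.
- **Gap of more than 45 days.** On-treatment ends at the earlier of 105 days after the last regular dose or "1 day before the first dose of cemiplimab re-treatment". Protocol 10.4.5.1 agrees, with "the day before their first cemiplimab retreatment dose" as the limit.

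The post-treatment period begins the next day and is given no end. TEAEs are "AEs that developed or worsened during the on-treatment period and treatment-related AEs that occur during post-treatment period". The remaining events are covered by "Post-treatment AEs are defined as AEs that developed or worsened during the post-treatment period and are not considered drug related by the investigator", and for their reporting the SAP says "Pre-treatment AEs and post-treatment AEs will be listed separately". Neither document defines a retreatment period, a retreatment denominator or a retreatment AE table.

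**The concern.** A patient on retreatment is receiving the study drug again, yet with a gap of more than 45 days the plan treats that time as post-treatment. Whether an event then reaches the SAP's TEAE tables depends on the investigator's causality call in an open-label study. Related events are pooled with those of the first course; unrelated events are not tabulated there. The tables therefore describe neither the first course alone nor all time on drug.

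What is at stake is the planned evidence on re-exposure. The study's end is defined by the last retreated patient completing retreatment and 105 days of safety follow-up, and PK and ADA samples are not routinely required during retreatment. AEs and laboratory results are the main safety evidence from that time, and no SAP table presents them coherently.

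**Working it through.** **1. Length of the two courses** (SAP 2.4; protocol 5.1 and 8.1.5)

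- First course: 5 × 9 + 4 × 12 = 93 weeks, as stated; 5 × 3 + 4 × 4 = 31 doses.
- Retreatment: 4 × 12 = 48 weeks, as stated; 4 × 4 = 16 doses.
- The last of 16 doses, 21 days apart, falls 15 × 21 = 315 days after the first. To 105 days after it, counting both end days: 315 + 105 + 1 = 421 days, or 421 / 7 = 60.1 weeks.
- Share of on-drug weeks for a patient who completes both courses: 48 / (93 + 48) = 34%. This is a per-patient maximum.

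**2. The SAP 5.9.1 rules applied**

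Let g be the days from the last regular dose to the first retreatment dose. On-treatment ends, in days after the last regular dose, at g + 315 + 105 if g ≤ 45 (full retreatment course), and at the smaller of 105 and g − 1 if g > 45. An AE x days after the first retreatment dose falls on day g + x. If g > 45, that day is always later than g − 1, so no retreatment AE is on-treatment. AEs at x = 0, 100 and 400 gave the same class within each row:

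| g (days) | On-treatment ends (day) | Unrelated AE on retreatment | Related AE on retreatment |
|---|---|---|---|
| 30 | 450 | TEAE | TEAE |
| 45 | 465 | TEAE | TEAE |
| 46 | 45 | listing only | TEAE |
| 77 | 76 | listing only | TEAE |
| 105 | 104 | listing only | TEAE |
| 200 | 105 | listing only | TEAE |

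For g from 46 to 105, retreatment also shortens the first course's own 105-day window, by 105 − (g − 1) days. At g = 77 that is 105 − 76 = 29 days. An unrelated AE in those days would have been a TEAE had the patient not been retreated.

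**3. How often the 45-day exception can apply** (protocol Tables 5 and 6)

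The last regular dose is cycle 9 day 64, and the first follow-up visit with scheduled tumor assessment is Follow-up 2.

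- If the cycle 9 visit means day 85: (85 − 64) + 28 + 28 = 77 days after the last dose (57 to 97 with visit windows).
- If it means the day-64 dose (an assumption): 28 + 28 = 56 days (42 to 70 with windows).

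The footnote to Table 6 lets the scan precede the visit by up to 14 days, but re-consent and repeat screening must follow before dosing. A gap of 45 days or less is possible but should be uncommon.

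**4. Which outputs are affected when g > 45**

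| Output | Retreatment findings |
|---|---|
| SAP 5.9.1: all, serious, Grade 3 or higher, discontinuation and fatal TEAEs | related only, pooled with the first course |
| SAP 5.9.2 worst-grade and laboratory shift; 5.9.4 ECG shift; 5.9.5 physical exam | omitted, whatever the causality |
| SAP 5.9.1 post-treatment AE listing | unrelated AEs |
| Protocol 10.4.5.1: deaths and SAEs; Grade 3/4 events | not expressly limited to TEAEs |

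SAP 5.7 does not say whether retreatment doses count towards exposure, so event counts and exposure may not cover the same time.

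**The case against.** The strongest defence is that this is a presentation rule on which protocol and SAP agree, and that no data are lost. All AEs are collected regardless of relationship to 105 days after the last study treatment (protocol 9.4.1), listings carry start dates and study days, and the IDMC reviews accumulated safety data. That stands. It limits the point to how the data are summarised.

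A reader might infer that unrelated deaths and SAEs on retreatment can only ever be listed. The documents do not support that. Protocol 10.4.5.1 plans summaries of deaths and SAEs, and of Grade 3 and 4 events, without confining them to TEAEs, and SAP 1.2.4 declares only added efficacy endpoints as departures from the protocol. What remains is that the SAP's own serious, fatal and Grade 3 or higher tables are TEAE tables.

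The causality dependence is not peculiar to retreatment: it applies to every patient after the on-treatment period, and SAP 6.4 counts a missing relationship as related. That is reasonable for patients off drug. It is less so for patients being dosed again.

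Keeping retreatment out of the first-course tables would be defensible, but the rule does not do that, because related retreatment events are admitted. Removing them outright carries its own risk: protocol 9.4.3 notes that irAEs can appear several months after the last dose, so a late first-course irAE could leave the main tables.

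Timing also limits the effect at the primary analysis. That cut comes about 57 weeks after the last patient's first dose, and retreatment requires 93 completed weeks. Only patients dosed at least 93 − 57 = 36 weeks before the last one could even have finished the first course by then.

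**Conclusion.** The point holds on the condition that retreatment starts more than 45 days after the last regular dose. The SAP's TEAE tables then combine related events from both courses with unrelated events from the first course only, and the worst-grade, shift and physical-exam summaries leave retreatment out. This follows from the definitions and needs no assumption about event rates.

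The size is known per patient but not for the study. Up to 421 days per retreated patient fall outside the on-treatment period. It would be wrong to read the 34% as the share of safety data missing from the tables: it is the on-drug share for one patient who completes both courses, and the number retreated is not given. That number is probably small, given the eligibility conditions. It would also be wrong to say that all retreatment is affected, since a gap of 45 days or less is handled consistently. That this exception is uncommon rests on progression usually being found at scheduled imaging, and on how the cycle 9 visit is read.

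The rule should be changed because it gives an incoherent summary for patients back on drug, not because it is likely to alter the overall safety picture.

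**What to change.** In SAP 5.9.1 and protocol 10.4.5.1, for retreatment that starts more than 45 days after the last regular dose:

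1. Define a retreatment period, from the first retreatment dose to 105 days after the last retreatment dose.
2. Add one set of tables with retreated patients as the denominator, covering all AEs, SAEs, deaths and worst laboratory grades in that period regardless of causality.
3. In the main TEAE tables, identify the related events that began in the retreatment period, for example by footnote, rather than removing them.

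The cost is a wording change and one small extra table set. The data are already collected under the protocol.

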5.9.2. Clinical Laboratory Measurements and Vital Signs

Listings of laboratory measurements will include laboratory values, normal ranges, grade (if applicable), collection date, and visit. For numeric lab variables and change from baseline to each visit will be summarized.

Summary tables for worst laboratory values during on-treatment period with NCI CTCAE all grade and grade ≥ 3 will be generated. Shift tables from baseline to worst post-treatment NCI CTCAE grade during on-treatment period will be generated.

5.9.3. Analysis of Vital Signs

Vital signs (pulse, sitting blood pressures, and temperature) will be listed and summarized by Baseline and change from Baseline to each scheduled assessment time with descriptive statistics.

5.9.4. Analysis of 12-Lead ECG

ECG parameters (PR interval, QT interval, QTc interval if applicable, QRS interval, and Ventricular rate) will be listed and summarized by Baseline and change from Baseline to each scheduled assessment time with descriptive statistics.

ECG status (i.e. normal, abnormal not clinically significant, and abnormal clinically significant) will be reported. Shift tables from baseline to worst post-baseline findings (normal, abnormal not clinically significant, and abnormal clinically significant) during on-treatment period will be generated.

5.9.5. Physical Exams

Physical examination findings at baseline as well as post-baseline findings by body system and status (normal, abnormal not clinically significant, and abnormal clinically significant) will be listed. Number and proportion of patients with new or worsened physical exam abnormalities during on-treatment period will be summarized.

5.10. Analysis of Pharmacokinetic and Antibody Data

5.10.1. Analysis of Pharmacokinetic Data

Concentration of cemiplimab in serum will be assessed at multiple time points throughout the study treatment and follow-up periods, and the PK variables will be determined.

Summaries of study drug concentrations will be presented by nominal time point (ie, the time points specified in the protocol) and group. Pharmacokinetic variables, including C_{eoi} and C_{trough} , will be presented as individual values with descriptive statistics.

5.10.2. Analysis of Immunogenicity Data

The immunogenicity variables described in Section 4.6.2 will be summarized using descriptive statistics. Immunogenicity will be characterized by ADA responses and titers observed in patients in the ADA analysis set. ADA response categories and titer categories are defined as follows:

Anti-drug antibody response categories and titer categories that will be assessed are as follows:

- Pre-existing immunoreactivity, defined as either an ADA positive response in the cemiplimab ADA assays at baseline with all post first dose ADA results negative, or a positive response at baseline with all post first dose ADA responses less than 9-fold over baseline titer levels.
- Persistent Response-Treatment-emergent ADA positive response with two or more consecutive ADA positive sampling time points, separated by at least 12-week period (based on nominal sampling time), with no ADA negative samples in between, regardless of any missing samples.
- Indeterminate Response –Treatment-emergent ADA positive response with only the last collected sample positive in the ADA assay, regardless of any missing samples.
- Transient Response –Treatment-emergent ADA positive response that is not considered persistent or indeterminate, regardless of any missing samples.
- The treatment-emergent responses will be further characterized as Persistent, Indeterminate, or Transient

- Treatment boosted ADA response, defined as a positive response in the cemiplimab ADA assay post first dose that is greater than or equal to 9-fold over baseline titer levels, when baseline results are positive.
- Titer value category (Titer Range)
 - Low (titer <1,000)
 - Moderate ($1,000 \leq \text{titer} \leq 10,000$)
 - High (titer >10,000)
 - NAb response in ADA positive patients

Listing of all ADA titer levels will be provided for treatment-emergent and treatment-boosted ADA response patients.

Potential association between immunogenicity variables and systemic exposure to cemiplimab will be explored by treatment groups. Plots of cemiplimab concentrations may be provided for analyzing the potential impact of ADA response status, titer and on PK.

Potential association between ADA/immunogenicity variables and safety may be explored with a primary focus on the following safety events during the TEAE period:

Infusion related reactions (serious or severe and lasting 24 hours or longer)

Hypersensitivity

Anaphylaxis

Potential association between immunogenicity variables and efficacy endpoints may be explored (e.g. scatter plot or spaghetti plot).

5.11. Analysis of Exploratory Biomarker Data

Descriptive statistics of ORR will be provided by PD-L1 expression levels (for example, PD-L1 expression <1% vs PD-L1 expression $\geq 1\%$). Descriptive statistics of TMB will be provided by patients' clinical efficacy data.

Description of statistical methods that will be used for additional biomarker data analyses will be provided in a separate Biomarker Analytical Plan.

6. DATA CONVENTIONS

The following analysis conventions will be used in the statistical analysis.

6.1. Definition of Baseline for Efficacy/Safety Variables

Unless otherwise specified, the Baseline assessment for all measurements will be the latest available valid measurement taken prior to the administration of investigational product.

6.2. Data Handling Convention for Efficacy Variables

Patients who are deemed NE according to RECIST version 1.1. or unevaluable by the composite response criteria will be considered as not reaching PR/CR in calculating ORR, i.e. they are not considered as responders in the numerator of ORR, but they are counted in the denominator of ORR.

6.3. Definition of Study Day

Study day 1 is the day of patient receiving first dose of cemiplimab. Study day -1 is the day before patient receiving first dose of cemiplimab. There is no Day 0.

For events prior to the first day a patient receiving cemiplimab treatment, the study day is defined as date of the date of event - first dose of cemiplimab; for events on or after the first dose of cemiplimab, the study day is defined as date of event - date of the first dose of cemiplimab +1.

6.4. Data Handling Convention for Missing Data

No missing data imputation is planned in this study unless specified otherwise.

For categorical variables, patients with missing data are not included in calculations of percentages unless otherwise specified. When relevant, the number of patients with missing data is presented.

Medication missing/partial dates

To determine whether a medication is prior, concomitant or post-treatment medication, the missing medication start date is estimated as early as possible up to date of the first study treatment, and the missing medication end date is estimated as late as possible. If the medication start date is missing, the onset day will not be imputed in medication listings.

Date of first / last study treatment

Date of first infusion is the first non-missing start date of dosing filled in the CRF "Investigational Product" module.

AE suspected to be caused by cemiplimab If AE suspected to be caused by cemiplimab is missing, the AE relationship will be imputed as related.

6.5. **Unscheduled Assessments**

Unscheduled visit measurements may be used to provide a measurement for a baseline or endpoint value if appropriate according to their definition. The measurements may also be used to determine abnormal laboratory or ECG values.

The determination of baselines and worst post-baseline values for both efficacy and safety variables will be based on scheduled available assessments and unscheduled available assessments.

Extra assessments (laboratory data or vital signs associated with non-protocol clinical visits or obtained in the course of investigating or managing adverse events) will be included in listings, but not by visit summaries except for the endpoint determination. If more than one laboratory value is available for a given visit, the first observation will be used in summaries and all observations will be presented in listings.

7. **MULTIPLICITY CONSIDERATIONS**

Patients will be enrolled into 2 separate groups according to the stage of disease: metastatic BCC (Group 1) or unresectable locally advanced BCC (Group 2). Statistical analyses for Group 1 and Group 2 will be conducted and reported separately; ie, efficacy results and clinical conclusions from Group 1 will not affect those of Group 2, and vice versa. A separate type I error of 5% is applied to Group 1 and Group 2, respectively. Therefore, statistical control of overall type I error for the whole study is not planned.

